30.04.2023

Evaluation of the Effects of A-Prf and Oral Dexamethasone Use on Postoperative Complications in Third Molar Tooth Extraction

Study Protocol

This study was conducted on 30 patients who were referred to XXX Oral and Maxillofacial Surgery Clinic and were indicated for extraction of impacted third molars. After clinical and radiographic evaluations of all patients, bilateral similarly positioned lower wisdom teeth with full mucosal retention were included.

The tooth extraction on one side of each patient constituted a study group and the other tooth extraction constituted the control group. In Group 1, A-PRF was placed in the patients' tooth extraction sockets and the flap was closed primarily using 3/0 silk suture. The patients were formed into Group 2 so that the other tooth would be extracted 5 weeks later. In Group 2, primary closure was achieved with 3/0 silk suture without placing any biomaterial in the extraction socket, and after the procedure, the patient was prescribed oral dexamethasone (Dekort 4 mg tablet, S:3*1 DEVA brand) with the statement that it would be used for 3 days.

Surgical Technique and Application

Before the operation, the patients included in the study had their radiological orthopantomography taken and their clinical examinations were performed.

The impacted wisdom teeth of the patients were extracted under local anesthesia after determining which tooth would be extracted first and which group it would be included in a random manner. The patient was administered local anesthesia with 1/100,000 epinephrine containing Ultracain D-S Forte® (Sanofi Aventis, Istanbul-Turkey) and after mandibular, lingual and buccal anesthesia, an envelope incision was made and the flap was lifted. Depending on the position of the tooth, the tooth was removed by separating or dividing it when necessary.

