Before the operation where the surgical area where A-PRF would be applied was located, 1 tube, 10 cc (Ayset tube, Ayset Tibbi Ürünler San. A.Ş., Adana/Türkiye) of blood was taken by the assistant personnel. Blood collection was performed via the peripheral antecubital vein by selecting the appropriate intracatheter for the patient's vascular structure. Care was taken to ensure that the patient was in a comfortable position during blood collection. The collected blood was centrifuged for 14 minutes at 1500 rpm using a centrifuge device (Intra-Lock Intra-Spin L-Prf Device, Intra-Lock International, Inc., FL, USA). The A-PRF obtained at the end of centrifugation was placed in the embedded wisdom tooth extraction cavity and the region was closed primarily.

All patients were prescribed amoxicillin 1000 mg (Largopen 1000 mg, 3*1), ibuprofen 600 mg (Brufen 600 mg, 2*1), benzydamine hcl + chlorhexidine gluconate mouthwash (Chloroben 200 ml mouthwash, 3*1) after the operation. They were asked to use the antibiotic and mouthwash as recommended and to take painkillers when needed. The sutures were removed 1 week later.

The VAS scale was used for the patients' pain assessments. Patients were instructed on how and at what times to fill out the scale, and were asked to fill in the scores from 0 to 10 (0, no pain; 10, unbearable pain) at hours 3, 6, 9, 12, and 24 and days 2, 3, 4, 5, 6, 7, 14, and 30. In order to evaluate the patients' analgesic use, patients were asked to note their additional analgesic use on the forms given to them.

For the patients' edema evaluations, the angulus-tragus, angulus-lateral canthus, angulus-nasal wing, angulus-labial commissure, angulus-pogonion face measurements were made before the operation, on the 2nd day after the operation, on the 7th day, 14th day, and 30th day after the operation. For the patients' trismus evaluations, the maximum mouth opening and the distance between the incisal edges of the central teeth in the most open position of the mouth were measured before the operation, on the 2nd day after the operation, on the 7th day, 14th day, 14th day, and 30th day after the operation.

Statistical Analyses

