While evaluating the findings obtained in the study, NCSS (Number Cruncher Statistical System) 2020 Statistical Software (NCSS LLC, Kaysville, Utah, USA) program was used for statistical analysis. While evaluating the study data, quantitative variables were shown with mean, standard deviation, median, min and max values, and qualitative variables were shown with descriptive statistical methods such as frequency and percentage. Shapiro Wilks test and Box Plot graphics were used to evaluate the conformity of the data to normal distribution. Wilcoxon Signed Ranks Test was used in intra-group comparisons of parameters that did not show normal distribution, and Dunn was used to determine the group causing the difference. The results were evaluated at a confidence interval of 95%, and significance was at the level of p<0.05.

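### The analysis section states no A-PRF versus dexamethasone test in plain words: *intra-group* is ambiguous, Dunn does not fit two paired groups, and variables that pass the normality check have no stated test

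*Combined protocol and SAP*

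**What the plan says.** The Study Protocol section describes a split-mouth design. "This study was conducted on 30 patients", and "The tooth extraction on one side of each patient constituted a study group and the other tooth extraction constituted the control group". Group 1 is A-PRF in the socket; Group 2 is no biomaterial plus oral dexamethasone. The groups are therefore the two treatments, and every patient belongs to both.

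The Surgical Technique and Application section sets out the outcomes:
- pain on a 0–10 VAS "at hours 3, 6, 9, 12, and 24 and days 2, 3, 4, 5, 6, 7, 14, and 30";
- five facial distances and mouth opening, before the operation and on days 2, 7, 14 and 30;
- analgesics: "patients were asked to note their additional analgesic use on the forms given to them".

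The Statistical Analyses section is one paragraph. On choice of test it says:
- on checking distributions: "Shapiro Wilks test and Box Plot graphics were used to evaluate the conformity of the data to normal distribution";
- on the only comparison test that it names: "Wilcoxon Signed Ranks Test was used in intra-group comparisons of parameters that did not show normal distribution";
- on the follow-up step after that test: "Dunn was used to determine the group causing the difference";
- on categorical data: "qualitative variables were shown with descriptive statistical methods such as frequency and percentage".

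It sets significance at p<0.05. It names no other hypothesis test.

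**The concern.** The title question is how A-PRF and oral dexamethasone affect postoperative complications, so the result that matters is one treatment against the other within the same patient. A reader of the analysis section cannot tell which p-value answers it.

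If the signed-rank test was applied only over time within each treatment, no stated result answers it. Two separate findings of significant change do not amount to a comparison of the changes. The Dunn step adds confusion because it speaks of finding a group when there are only two. The normality check sorts variables into two branches, but only one branch leads to a test.

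**Working it through.** The documents give no SD, effect size, correlation or power figure, so there is no stated figure to reproduce. Steps 1 to 3 are readings of the text. Steps 4 and 5 are illustrations on stated assumptions.

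**1. What *intra-group* can mean.** The groups are the treatments (Study Protocol).
- Literal reading: within one treatment, hence time against time. No treatment comparison is stated.
- Loose reading: within patient, hence A-PRF against dexamethasone. The signed-rank test is a paired test and suits this contrast.

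The text does not decide between them.

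**2. What Dunn could locate.** The number of pairs among k items is k(k−1)/2.
- Two groups: 2×1/2 = 1 pair. There is nothing to locate after a difference is found.
- Thirteen VAS times: 13×12/2 = 78 pairs.
- Five edema or trismus times: 5×4/2 = 10 pairs.

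A Dunn-type procedure could serve the last two after a Friedman test. No omnibus test is named, however, and the text says group, not time. In its usual form Dunn also treats groups as independent.

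**3. Where the normality check leads.**

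| Variable | Stated test |
|---|---|
| Quantitative, not normal | Wilcoxon signed-rank (*intra-group*), then Dunn |
| Quantitative, normal | none |
| Qualitative | none (frequency and percentage only) |

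The second row is empty under either reading of step 1.

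**4. Why within-treatment tests cannot answer the question.** Assumptions: 30 patients; two-sided 5%; normal changes with SD 1 for each operation; correlation between a patient's two operations of 0/0.3/0.5/0.7; 40,000 simulated trials per setting; exact signed-rank critical value T ≤ 137 (actual level 4.97%). A mean change of 1.0 SD lies √30 × 1.0 = 5.48 standard errors from zero.

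| True mean changes | Both treatments significant over time | Paired A-PRF v dexamethasone test significant |
|---|---|---|
| 1.0 and 1.5 SD | 99.9% | 45/59/74/92% |
| 1.0 and 1.0 SD | 99.9% | about 5% |

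The within-treatment column is the same in both rows; the paired column tells them apart.

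**5. Dunn, if it was run as an unpaired two-group test (the text does not say so).** Such a test uses a variance of 2/n for the difference, where the true one is 2(1−ρ)/n. With no true difference, the rejection rate is therefore about 2Φ(−1.96/√(1−ρ)), which is 5/1.9/0.6/0.03% at ρ = 0/0.3/0.5/0.7. Simulating the rank test itself gives about 5/2/0.7/0.1%. The test is thus conservative when the operations are positively correlated.

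Its effect on power depends on the outcome distribution:

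| Assumed outcome | Unpaired Dunn | Paired signed-rank |
|---|---|---|
| Normal, paired effect 0.53 SD of the difference | 79/67/51/24% | 78% |
| Skewed 0–10 pain, means 3 v 4, SD 2 | 57/58/59/62% | 48/62/74/91% |
| Skewed 0–10 pain, means 1.5 v 2.5, SD 1.5 | 86/90/92/96% | 74/85/93/99% |

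**6. How many contrasts are affected.** VAS 13, plus facial distances 5×4 = 20, plus mouth opening 4, gives 37. The sentence on trismus can be read as two measures, mouth opening and interincisal distance; then 13 + 20 + 8 = 41. Day 14 is listed twice for trismus and is counted once here.

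**The case against.** The strongest reply is that the only comparison test named is a paired one, in a split-mouth design, and that the mention of a group causing the difference suggests groups were compared. The loose reading therefore has real textual support. This stands: on that reading the treatment test is suitable, and what remains is unclear wording, a Dunn step without a purpose and no rule for normal variables.

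Three stronger claims are tempting, and the documents support none of them.
- *No paired comparison was made, or the wrong test was run.* The text is ambiguous. It does not show what was done.
- *Dunn cost the trial power.* Nothing says that it was run unpaired. Even if it was, the direction is not fixed: in step 5 it has the higher power in three of the eight skewed-pain settings (57 v 48, 86 v 74, 90 v 85).
- *Analgesic use has no test.* The signed-rank rule covers non-normal parameters without listing outcomes, so a non-normal analgesic count falls under it just as VAS does. It would be descriptive only if recorded as a qualitative variable, which the protocol does not say.

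It can also be said that the 99.9% figures come from large assumed changes. That is so. They illustrate the principle that within-treatment tests do not compare treatments; they do not estimate what happened in this trial.

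Finally, the gap for normal variables matters only if some variable passed the check. That is true, but the plan should still say what was then done.

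**Conclusion.** The concern holds as a fault of specification. Taken literally, the analysis section tests change over time within each treatment and states no A-PRF versus dexamethasone comparison; taken loosely, it names a suitable paired test in the wrong words. The Dunn step and the missing test for variables judged normal are faults under either reading.

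The missing or unclear text is certain; the harm is conditional. If only within-treatment tests were run, the title question has no valid answer, and with large changes over time both treatments would be significant whether or not they differ. If the paired contrast was run, the damage is confined to reporting. All percentages rest on assumed SDs, effects and correlations. The choice of primary endpoint and multiplicity across the 37 (or 41) contrasts are separate matters that this point does not settle. It should be fixed.

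**What to change.** First ask the sponsor which comparison the signed-rank test made, what Dunn compared, and what was used for variables judged normal. Keep the answer on record. Then replace the test sentences with:

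> At each time point the A-PRF and dexamethasone operations of the same patient are compared on the within-patient difference by the Wilcoxon signed-rank test, for all quantitative outcomes whether or not they pass the normality check, with an estimate and 95% CI. Conclusions about treatment rest on this contrast; within-treatment comparisons over time are descriptive.

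In addition:
- State the quantity compared. Change from the preoperative value is a reasonable option for edema and trismus; VAS has no preoperative value, so the raw score is used.
- State whether analgesic use is analysed as a count under the same rule.
- Delete Dunn, or confine it to time-point comparisons after a Friedman test within one treatment.
- Label the paired contrast post hoc if it is newly chosen after data collection.

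The cost is one query and revised wording. A small reanalysis of existing data is needed only if the paired contrast was not run; no new patients or measurements are needed. Using signed-rank throughout loses little when data are normal. At its efficiency of 0.955, 30 pairs act like 30 × 0.955 = 28.65, and the difference detectable with 80% power at two-sided 5% moves from 2.802/√30 = 0.51 to 2.802/√28.65 = 0.52 SD of the within-patient difference. In return, the choice of test no longer depends on a normality check.

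### Dunn is named as the follow-up to a two-condition signed-rank test; it has nothing to locate between two paired groups, and for change over time its meaning, the omnibus test, the contrasts and the adjustment are not stated

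*Combined protocol and SAP*

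**What the plan says.** The Statistical Analyses section contains one inferential rule. Its first half is "Wilcoxon Signed Ranks Test was used in intra-group comparisons of parameters that did not show normal distribution". Its second half is "Dunn was used to determine the group causing the difference". The only threshold is that "significance was at the level of p<0.05". No test for three or more related measurements is named. Nor are a version of Dunn, a set of contrasts or a multiplicity adjustment.

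The Study Protocol section defines two groups within each patient: "The tooth extraction on one side of each patient constituted a study group and the other tooth extraction constituted the control group".

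The Surgical Technique and Application section gives the measurement times. VAS pain is scored "at hours 3, 6, 9, 12, and 24 and days 2, 3, 4, 5, 6, 7, 14, and 30". For edema, the "face measurements were made before the operation, on the 2nd day after the operation, on the 7th day, 14th day, and 30th day" after surgery. Mouth-opening distances "were measured before the operation, on the 2nd day after the operation, on the 7th day, 14th day, 14th day, and 30th day", with day 14 printed twice.

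**The concern.** A post-hoc test finds which of three or more levels differ after an overall test has shown that some do. The signed-rank test is not an overall test of that kind. It compares two paired conditions, and its result already identifies the pair. The two halves of the rule therefore do not fit together.

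The wording also points two ways. Comparisons within a group suggest change over time within one treatment. A search for the group responsible suggests three or more groups, which this trial does not have. If the comparison meant is the A-PRF side against the dexamethasone side, signed-rank is suitable and Dunn is redundant.

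At stake are the statements about how pain, edema and mouth opening change over time within each treatment. A reader cannot tell which procedure produced them, and the possible procedures give different answers.

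**Working it through.** The documents give no sample-size derivation, SD, correlation or effect size, so there is no stated figure to reproduce. The counts below come from the documents. The power and error figures are illustrations under stated assumptions.

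**Inputs from the documents.**
- Patients: 30. Paired groups: 2 (Study Protocol).
- VAS times: 5 in hours + 8 in days = 13. None is pre-operative.
- Edema times: pre-operative and days 2, 7, 14, 30 = 5.
- Mouth-opening times: 6 printed, 5 distinct once the repeated day 14 is counted once.
- Threshold: 0.05, with no adjustment stated.

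**Number of pairs, k(k−1)/2.**
- 2 groups: 2×1/2 = 1. Nothing is left to locate.
- 5 times: 5×4/2 = 10.
- 13 times: 13×12/2 = 78.

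Three readings of Dunn over time follow.

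**Reading 1: a rank-based Dunn test.** In the pooled (Kruskal-Wallis) form, the standard error of a difference in mean ranks is √[N(N+1)/12 × 2/n]. With n=30 and N=30×5=150, this is √[150×151/12 × 2/30] = √125.8 = 11.2. The formula treats all 150 values as independent, so it is too large when a patient's values are positively correlated. The Friedman form ranks within each patient, with standard error √[k(k+1)/(6n)] = √[30/180] = 0.41 on its own scale.

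Assumed: normal data, equal spread, exchangeable correlation, a 0.3 SD change at one of 5 times, one pair tested at two-sided 5%, 4000 simulated trials per cell.

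| Correlation | Pooled Dunn | Friedman-form Dunn | Signed-rank |
|---|---|---|---|
| 0.3 | 17% | 22% | 26% |
| 0.5 | 13% | 29% | 35% |
| 0.7 | 8% | 43% | 52% |
| 0.9 | 3% | 89% | 94% |

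With no true change and correlation 0.7, pooled Dunn rejects about 0.2% of the time; the other two reject about 5%. At a 1 SD change all three reach 97% or more, so the loss concerns small changes.

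**Reading 2: pairwise signed-rank tests at 0.05 with no adjustment.** If the tests were independent, the familywise error would be 1 − 0.95^m: 0.40 for m=10 and 0.98 for m=78. The tests share data, so simulation at n=30 is the better guide. It gives about 30% for 5 times and about 80% for 13 (78 to 84% across runs and assumptions), and the within-patient correlation hardly matters. For contrasts with the first time only, the figures are about 15-16% (4 contrasts) and 33-35% (12 contrasts).

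**Reading 3: signed-rank p-values with a Dunn-Bonferroni adjustment.** The per-test level is 0.05/10 = 0.005 or 0.05/78 = 0.00064. Simulated familywise error is about 3-5% for 5 times and 1.5-2.5% for 13. Error is controlled.

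**The case against.** The strongest reply is that Dunn here means the Dunn-Bonferroni adjustment. The sentence joins signed-rank and Dunn, which fits that reading. The procedure would then be sound and close to the one recommended below. This stands as a possibility. The text does not say so, however, and even then it leaves the family of contrasts open, on which the per-test level depends (0.005 or 0.00064 over all pairs).

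A second reply is that the simulations depend on chosen scenarios. That is true. The incoherence follows from the tests and the design alone, and the figures show only what could follow from it. Signed-rank is not free of assumptions either. With skewed data, equal medians and unequal spread (log-SD 0.3 against 0.9), it rejected 13-14% of the time in a check.

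Third, Friedman followed by its own form of Dunn is a coherent procedure, and it holds about 5% error with equal spread. That is fair, but the plan names no Friedman test.

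Three stronger inferences are tempting, and the documents do not support them:
- *The treatment comparison is invalid.* Signed-rank suits two paired sides, and a redundant follow-up does not spoil it.
- *False positives did accumulate.* That holds only under Reading 2, which the text neither states nor excludes.
- *Dunn would miss the pain time course.* Under an assumed VAS profile falling to zero, both rank-based forms have only 0-3% power for a 0.3 SD change from hour 3 to hour 6. Under the same profile, hour 3 against day 3 keeps about 90-100%. The loss is confined to small early contrasts.

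Additional analgesic use is also recorded, with no schedule given. It might supply further repeated levels, but the plan says nothing that would make Dunn clearer there.

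**Conclusion.** The point holds, and it should be fixed. As written, the rule cannot be carried out for two paired groups and cannot be reproduced for the repeated times. Its effect is confined to change over time within a treatment and ranges with the reading: from a wording correction only (Dunn-Bonferroni), through a loss of power for small changes (pooled Dunn, about 8% against 52% in the illustration), to a familywise error of about 30% or 80% (unadjusted tests on all pairs). The documents do not show which applies. The counts of 2 groups and 5 or 13 times are certain, apart from treating the second day 14 for mouth opening as a duplicate. The percentages rest on n=30 and on assumed distributions, correlations and shifts.

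**What to change.** 1. **A-PRF versus dexamethasone.** State one paired within-patient test per endpoint and time: signed-rank on the within-patient difference where it is non-normal, with no Dunn step.
2. **Change over time within a treatment, non-normal data.** Replace the sentence with a Friedman test followed by Holm-adjusted paired signed-rank contrasts from a stated list. For edema and mouth opening, contrast each post-operative visit with that session's pre-operative value (4 contrasts). VAS has no pre-operative score, so give a short pre-specified list of pairs. A mixed model with only a random patient effect is not the natural substitute here, because it normally assumes normal residuals and the rule covers parameters selected for not being normal.
3. **Existing results.** The section is in the past tense, so report what Dunn was, which pairs were tested and what correction, if any, was applied. If it was Dunn-Bonferroni, correct the wording and name the contrasts.

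**Cost.** This is a small reanalysis of the same data, with nothing new to collect. Some small within-treatment changes may no longer reach significance. With one shifted time, a 0.5 SD change and correlation 0.5, signed-rank power falls from about 74% to 49% after Holm over 4 contrasts, and from about 73% to 32% over 12, which is the reason for a short VAS list. At 1 SD and correlations of 0.3 to 0.9 it stays at 96% or more over 4 contrasts and 89% or more over 12.

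### No primary outcome, key time point or error control is named, yet one p<0.05 rule covers roughly 21 to 37 possible treatment comparisons

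*Combined protocol and SAP*

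**What the plan says.** The Surgical Technique and Application section sets out four kinds of outcome.

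- **Pain:** VAS scores are recorded "at hours 3, 6, 9, 12, and 24 and days 2, 3, 4, 5, 6, 7, 14, and 30", which is 13 readings.
- **Edema:** "angulus-tragus, angulus-lateral canthus, angulus-nasal wing, angulus-labial commissure, angulus-pogonion face measurements were made before the operation", and again on days 2, 7, 14 and 30.
- **Trismus:** the measurement is "the maximum mouth opening and the distance between the incisal edges of the central teeth in the most open position of the mouth", before surgery and on days 2, 7, 14 and 30 (day 14 is printed twice).
- **Analgesic use:** "patients were asked to note their additional analgesic use on the forms given to them". No time point or analysis is given for it.

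The Statistical Analyses section names two procedures for comparisons. The first is given as follows: "Wilcoxon Signed Ranks Test was used in intra-group comparisons of parameters that did not show normal distribution". The second is a post hoc step, described only in these words: "Dunn was used to determine the group causing the difference". The section closes with the one decision rule: "The results were evaluated at a confidence interval of 95%, and significance was at the level of p<0.05".

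Nowhere in the document is an outcome called primary, a time point singled out, or a sample-size calculation given that would imply either. No hypothesis or success rule is stated, and the study is not described as exploratory.

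**The concern.** A single unadjusted threshold applied to many unranked outcomes and times lets any one of them be put forward as the trial's finding after the results are known. The 5% error rate a reader attaches to p<0.05 belongs to one pre-named test. It does not belong to the best of a couple of dozen.

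The Dunn procedure does not fill the gap. It is named to locate a difference within a comparison, so any adjustment inside it would not reach across pain, edema, trismus and analgesic use.

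At stake is whether a reported advantage of one treatment, such as on one facial line at one visit, can be told apart from chance.

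**Working it through.** The plan gives no familywise error, power or sample-size figure, so there is nothing of its own to reproduce. The check counts the comparisons the schedule allows and asks what the stated rule does across them.

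**Inputs from the documents**

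- Threshold per test: 0.05 (Statistical Analyses). Sidedness is not stated; two-sided is assumed, in line with the 95% interval.
- 30 patients, with one side per treatment (Study Protocol).
- VAS: 5 hourly + 8 daily = 13 times. Facial distances: 5. Postoperative visits for edema and mouth opening: 4, counting the repeated day 14 once.

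**Count of between-treatment tests (inferred, not stated in the plan)**

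- Each facial distance tested: 13 + 5 × 4 + 4 = 37.
- Facial distances combined: 13 + 4 + 4 = 21.
- Both counts leave out analgesic use and within-group changes over time, and take mouth opening as one measure. Adding one analgesic test to 37 gives 38. Reading the trismus sentence as two measures gives 37 + 4 = 41, and both additions give 42.

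**If the tests were independent and no true difference existed**

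P(at least one p<0.05) = 1 − 0.95^m

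| m | Result |
|---|---|
| 21 | 0.659 |
| 37 | 0.850 |
| 38 | 0.858 |
| 41 | 0.878 |
| 42 | 0.884 |

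The expected number of false positives, which does not depend on correlation, is 21 × 0.05 = 1.05 or 37 × 0.05 = 1.85.

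**Allowing for correlation (all correlations assumed; the documents give none)**

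With a common correlation ρ between all test statistics and c = 1.96, the chance is 1 − ∫ [Φ((c − √ρ·z)/√(1−ρ)) − Φ((−c − √ρ·z)/√(1−ρ))]^m φ(z) dz. Numerical integration gives:

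| ρ | 21 tests | 37 tests |
|---|---|---|
| 0.5 | 0.429 | 0.554 |
| 0.7 | 0.295 | 0.365 |
| 0.9 | 0.157 | 0.181 |
| 0.95 | 0.117 | 0.130 |

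A separate simulation of paired t-tests with n = 30 (20,000 runs) agrees closely: 0.44 and 0.57 at ρ = 0.5, 0.31 and 0.37 at 0.7, 0.16 and 0.19 at 0.9.

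A second pattern sets zero correlation across pain, edema and trismus, with correlation falling off by visit order and equal between facial sites (1,000,000 draws):

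| Correlation of adjacent visits and of facial sites | 21 tests | 37 tests |
|---|---|---|
| 0.5 | 0.607 | 0.768 |
| 0.8 | 0.473 | 0.574 |

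**If the late pain tests could not reach significance**

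By days 14 and 30 most VAS scores may be tied (an assumption). An exact two-sided Wilcoxon test cannot fall below 2/2^5 = 0.0625 with five non-zero pairs; with six it can reach 2/2^6 = 0.031. Dropping both days leaves 11 + 20 + 4 = 35 or 11 + 4 + 4 = 19 tests. If independent, the chance is 1 − 0.95^35 = 0.834 or 1 − 0.95^19 = 0.623. At ρ = 0.95 it is 0.129 or 0.115.

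**For comparison:** one named test at 0.05 gives 5%. A Bonferroni split would need p < 0.05/21 = 0.0024 or p < 0.05/37 = 0.00135.

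**The case against.** The strongest objection is that the count describes an analysis the plan does not set out. Wilcoxon is named only for intra-group comparisons, which in a split-mouth trial may mean side against side or change over time, and no between-treatment test is listed for any outcome. This stands. The count is conditional, and the unspecified between-treatment analysis is a gap of its own. It does not remove the omission, because a plan that neither lists nor ranks its tests leaves the choice of headline result open.

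The size is also uncertain. Every correlation is assumed and the figures take the complete null. At a common correlation of 0.99 the chance is only 7.5% (21 tests) or 7.9% (37 tests). That is still above 5%, and so high a correlation across pain, swelling and mouth opening is implausible, but the percentages remain illustrations. The trismus wording also reads most naturally as one measurement with its definition, so little weight belongs on 41 or 42.

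Unadjusted tests, reported in full, are defensible in a 30-patient exploratory study, and the plan does not say that one significant result makes the trial positive. That would be a good answer if the document called itself exploratory. It does not, and it declares significance at a fixed level.

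Last, the past tense suggests that a primary outcome can no longer be named in advance. If so, the remedy is a reporting rule rather than restored confirmatory status.

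**Conclusion.** The concern holds. That no primary outcome, key time point or error control across outcomes is stated can be read directly from the document, and confidence in that is high.

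Confidence in the size is lower. If each scheduled measure is compared between treatments at p<0.05 with no true difference, the chance of at least one false positive is 66% to 85% under independence and about 12% to 77% under the main assumed correlations. Neither end is a bound. The direction does not depend on the exact count or on whether the late pain tests are informative: every case examined exceeds 5%.

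This should be corrected. It puts the interpretation of the trial at risk, but wording and reporting can address it.

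**What to change.** First state whether outcome data have been examined. Then follow one of two routes.

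**A. Data already seen (the more likely case).** Report every scheduled between-treatment comparison with an estimate and 95% CI, label all results exploratory, and present no single time point or facial line as the trial's result.

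**B. Data not yet seen.** Name one primary outcome from data already collected. Test it once, within patient between the two sides, with a two-sided paired test at 0.05, an estimate and a 95% CI. All other outcomes and times become secondary or descriptive, with estimates and 95% CIs.

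One example for B is the time-weighted area under the VAS curve from hour 3 to day 7, which uses 11 of the 13 readings, with the handling of missing diary scores fixed beforehand. It has a drawback: of its 168 − 3 = 165 hours, 168 − 24 = 144 fall after hour 24, so the early readings carry little weight. Because patients were told "to take painkillers when needed", pain and analgesic use are linked. They should be reported together, with a prior statement of how a pain difference will be read if analgesic use differs the other way. The document does not rank pain first, so the investigators may instead name edema or mouth opening at one stated time. The simple paired test relies on the order of extraction having been randomised, as the surgical section describes.

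**Cost.** Only SAP or report wording changes, with no new data or patients. Under A the trial makes no confirmatory claim. Under B individual time points and facial lines lose confirmatory status, and the single test is confirmatory only if the data are truly unexamined.
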